7.1.5. Unscheduled Visits

If a subject returns to the clinic outside of the normal study visit windows, assessments will be made at the investigator's discretion. All study relevant unscheduled visit assessments will be recorded in the eCRF using the supplemental visit eCRF pages.

7.1.6. Sample Collection Procedures

Blood samples for clinical laboratory measurements should be collected and processed according to the central laboratory collection manual guidance or if collection is for local laboratory according to study site laboratory's standard procedure.

7.1.7. Safety Considerations

Based on the known clinical manifestations of mitochondrial diseases, PTC expects that many AEs could occur during the course of the trial that are known to be associated with disease natural history.

Both the preclinical and clinical safety profiles of vatiquinone have been favorable. To date, in over 523000 patient treatment days with vatiquinone there have been 7 SAEs assessed by the investigators to be probably or possibly drug-related.

Specific dose modification guidelines for INR are provided in Section [7.4.6](#).

Nonetheless, specific or supportive care as chosen by the investigator may be considered.

7.1.8. Rescue Medication Administration for Epilepsy

Use of rescue medications for epilepsy will be collected throughout the study and analyzed as a secondary study endpoint. The following standardized criteria should be used for use of rescue medications:

- Seizure lasting longer than 4 minutes
- Occurrence of status epilepticus
- Cluster of 15 or more seizures

7.1.9. Prohibited Medications

Subjects will be required to maintain a stable regimen of mitochondrial disease supplements from screening throughout the trial.

Anticoagulants such as vitamin K antagonists, Factor Xa inhibitors are not permitted during the course of the study because of the potential interaction with vatiquinone on vitamin K associated coagulation factor synthesis.

Cytochrome P450 inhibitors such as itraconazole have been demonstrated to significantly increase the plasma concentrations of vatiquinone (up to 2-fold). Cytochrome P450 inducers such as rifampin significantly reduce the plasma concentrations of vatiquinone (up to 50% less). Therefore, strong CYP inducers and inhibitors, including grapefruit/grapefruit juice and St John's wort extract, should be avoided during the course of the study.

- In case treatment with a CYP inhibitor is required during the course of the study, coagulation parameters should be monitored and vatiquinone dose should be reduced by 33% in case INR increases over 1.5×ULN or Common Terminology Criteria for Adverse Event (CTCAE) Grade 2.
- In the event that a CYP inducer is used, no adjustment of the study drug dose will be required because there are no safety concerns with CYP inducers.

No changes to the AED regimen (except for weight-based dose adjustments) will be allowed during the first 24-week period.

The use of artisanal (non-Epidiolex cannabidiol) cannabidiol therapies should continue to be excluded due to uncertainty regarding the quality and quantity of cannabidiol in the artisanal product.

7.1.10. End of Treatment Visits

End of treatment visit takes place at Study Week 72 and includes the assessments listed in Section 7.1.2.1. Subjects who have an ongoing AE/SAE at the time of study completion will be followed for up to 30 days, until the event resolves, or until the sponsor and the Investigator agree that further follow-up is not medically necessary.

7.1.11. Early Termination Study Visit

Subjects who terminate from the study after receiving first dose and prior to the completion of all scheduled visits should have the end of treatment visit assessments completed as soon as possible. Early termination study visit will include the assessments listed in Section 7.1.2.1. Subjects who have an ongoing AE/SAE at the time of study completion will be followed for up to 30 days, until the event resolves, or until the sponsor and the Investigator agree that further follow-up is not medically necessary.

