ⁱ Blood will be drawn for PK assessment predose and 1, 3, 4, and 8 hours postdose (prior to the next dose of vatiquinone) at Baseline and Week 24, and only 4 hours postdose at Weeks 48 and 72. For subjects weighing less than 10 kg, PK blood draw can be reduced to 2 timepoints per visit at the Baseline and Week 24 visits. Recommended timepoints are 0 (predose) hour and 4 hours postdose.

^j During the Screening Visit, the subject's caregiver will be trained on how to capture information in the seizure diary and hospital admissions log.

^k Serious adverse events will be assessed from the Screening Visit through 30 days following the last dose of study drug should be reported via the SAE report form to PTC within 24 hours of becoming aware of the event(s). In addition, the AE portion of the eCRF must also be completed.

^l The follow-up contact will be by telephone and should be completed 30 days (± 7 days) post last study drug administration or termination visit, whichever is later. Adverse events and SAEs will be followed until resolution or until they have normalized. At the investigator's discretion an office visit and additional tests may be conducted in order to ensure proper follow-up of an AE/SAE.

^m First dose for the placebo-controlled phase of the study will be taken the same day as the Baseline Visit. Study drug will be dispensed during the Baseline Visit and at each subsequent in-person visit. Drug may be delivered via delivery service if needed.

ⁿ From Week 24 onwards, vatiquinone will be dispensed to all subjects entering the long-term extension phase. Vatiquinone will be dispensed after completing the Week 24 assessments. The subjects will enter the open-label phase of the study and receive vatiquinone for the dose after the visit.

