7.1.2.1. Baseline Visit/Randomization

The following assessments and procedures will be performed at Baseline Visit:

1. Review of all previous screening testing performed on the subject
2. 12-lead ECG at 4 hours postdose time-matched to pharmacokinetic (PK) blood collection; ECG should be performed approximately within 10 minutes preceding the 4-hour PK blood collection
3. Weight and oxygen saturation
4. Physical Examination including vital signs
5. Urine or serum pregnancy test: WOCBP must have a negative urine or serum pregnancy test (see Section 7.4.3)
6. Laboratory assessments for hematology, coagulation, serum chemistry, and urinalysis (see Section 7.4.2)
7. Randomization
8. The study drug will be administered at Baseline Visit by site staff or caregiver will be trained to administer the first dose on site
9. Blood samples drawn for PK analysis predose and 1, 3, 4, and 8 hours postdose (prior to the next dose of vatiquinone). For subjects weighing less than 10 kg, PK blood draw can be reduced to 2 timepoints per visit. Recommended timepoints are 0 (predose) hour and 4 hours postdose.
10. AE/SAE assessment
11. Concomitant medications assessment
12. Review of seizure diary
13. Calculation of total hospital admissions and total hospital days for disease-related issues from the time of the Screening Visit
14. CarerQoL-7D questionnaire
15. PedsQL questionnaire
16. Dispense study drug

During the Baseline Visit, study medication will be dispensed to the subject according to the randomization. First dose for the study drug will be taken the same day as Baseline Visit and PK samples collected during the Baseline Visit.

Subjects randomized to the treatment arm will be required to take study drug in a formulation mixed with sesame oil NF. Subjects in the placebo group will receive sesame oil with a colorant, which will have similar appearance and consistency as vatiquinone. In case the subject has a gastrostomy tube or nasogastric tube (G-tube or nasogastric tube) installed, vatiquinone or placebo will be administered using an amber oral dispenser into the G-tube with liquid food. If the subject is able to swallow, vatiquinone or placebo can be administered using an amber oral dispenser along with food.

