7. EEG
8. AE/SAE assessment
9. Concomitant medications assessment
10. Review of seizure and dosing drug diaries
11. Calculation of total hospital admissions and total hospital days for disease-related issues
12. CarerQoL-7D questionnaire
13. PedsQL questionnaire
14. Drug reconciliation of returned study drug bottles with dosing diaries
15. Informed consent if subject is continuing in Long-Term Extension phase
16. Dispense study drug if subject is continuing in Long-Term Extension phase

7.1.3. Long-Term Extension Phase (Study Weeks 36, 48, 60, and 72 are In-Person Visits and Study Weeks 28, 32, 40, 44, 52, 56, 64, and 68 are Telephone contact ± 1 week)

The subjects who are interested in continued treatment with vatiquinone will continue in the long-term extension phase of the study. In-person visits will occur every 12 weeks (± 1 week) and there will be every 4 weeks (± 1 week) telephone contact with the subject in between the in-person visits. Study medication will be dispensed at each in-person visit and will be sufficient to reach the next 12-week in-person visit.

The following assessments and procedures will be performed at each of the in-person visits under the long-term extension phase:

1. 12-lead ECG at 4 hours postdose time-matched to PK blood collection (Weeks 48 and 72 only; ECG should be performed approximately within 10 minutes preceding the 4-hour PK blood collection)
2. Weight and oxygen saturation
3. Physical examination including vital signs
4. Urine pregnancy test: WOCBP must have a negative urine pregnancy test (see Section 7.4.3). If a subject cannot perform a urine pregnancy test, a serum pregnancy test should be performed.
5. Laboratory assessments for hematology, coagulation, serum chemistry, and urinalysis (see Section 7.4.2)
6. Blood samples drawn for PK analysis 4 hours postdose at Study Weeks 48 and 72
7. EEG at Week 72
8. AE/SAE assessment
9. Concomitant medications assessment
10. Review of seizure and dosing drug diaries
11. Calculation of total hospital admissions and total hospital days for disease-related issues
12. CarerQoL-7D questionnaire will be collected at Study Week 48 and Study Week 72
13. PedsQL questionnaire (Week 72)
14. Drug reconciliation of returned study drug bottles with dosing diary (Study Weeks 36, 48, 60, and 72)
15. Dispense study drug (Weeks 36, 48, and 60)

The following assessments will be conducted at each of the telephone contacts and must include review of:

1. AE/SAE assessment

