7.3. PK and/or Other Assessments

Blood samples for PK assessments will be drawn predose and 1, 3, 4, and 8 hours postdose (prior to the next dose of study drug) at Baseline and Week 24, and 4 hours postdose at Week 48 and Week 72. For subjects weighing less than 10 kg, PK blood draw can be reduced to 2 timepoints per visit at the Baseline and Week 24 visits. Recommended timepoints are 0 (predose) hour and 4 hours postdose. The collection of these drug concentration values will serve 2 purposes: (1) to assess the consistency of systemic drug concentrations at specific timepoints around the time to maximum plasma concentration to confirm the durability of drug exposure and (2) be potentially incorporated in a structural model (from prior PK profiles) that can help to quantitate selected pharmacodynamic relationships such as safety and disease improving effects.

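### Protocol 7.1.11 (with 7.1.10) defines the early-termination visit by the Baseline/Randomization list instead of the Week 72 items, and no other text corrects this for early terminators

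*Protocol*

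**What the plan says.** Protocol 7.1.11 covers subjects who leave after the first dose and before all scheduled visits are done. It first says that they "should have the end of treatment visit assessments completed as soon as possible", and then: "Early termination study visit will include the assessments listed in Section 7.1.2.1". Protocol 7.1.10 defines the visit to which the first sentence refers: "End of treatment visit takes place at Study Week 72 and includes the assessments listed in Section 7.1.2.1".

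Section 7.1.2.1 is headed Baseline Visit/Randomization and has 16 items. They include review of screening tests, randomization, administration of the first dose (or training the caregiver to give it), review of the seizure diary and dispensing. The PK item reads: "Blood samples drawn for PK analysis predose and 1, 3, 4, and 8 hours postdose (prior to the next dose of vatiquinone". For subjects under 10 kg it allows two timepoints.

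The Week 72 content is set elsewhere:

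- Table 2, footnote i, asks for PK "only 4 hours postdose at Weeks 48 and 72".
- Section 7.1.3 has "Blood samples drawn for PK analysis 4 hours postdose at Study Weeks 48 and 72", and Section 7.3 repeats "4 hours postdose at Week 48 and Week 72".
- Section 7.1.3 also requires an EEG at Week 72, review of both the seizure and the dosing diary, and "Drug reconciliation of returned study drug bottles with dosing diary (Study Weeks 36, 48, 60, and 72".
- Dispensing in the extension falls at Weeks 36, 48 and 60, not at Week 72.

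**The concern.** A visit at which a subject leaves the trial should carry closing items: a final EEG, a last look at the dosing diary and a count of returned drug. The list that 7.1.11 names is built for entry. It asks for serial PK and lists none of those three.

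At stake is what sites do with children who stop early. Following the cross-reference adds blood draws with no stated purpose at that visit. It may also lose the exit EEG, which Protocol 7.4 counts among the safety evaluations, and the reconciliation of bottles against the dosing diary.

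**Working it through.** There is no power or alpha figure to reproduce. The check traces the cross-references, compares the lists and works out the PK volume.

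**1. Where the references lead.** Section 7.1.11 names 7.1.2.1 directly. Its other route, the end-of-treatment assessments, goes to 7.1.10, which names 7.1.2.1 again. Table 2 has columns for Screening, Baseline, each scheduled visit and Follow-up, and none for early termination.

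**2. Item comparison: 7.1.2.1 against Week 72 (Table 2, 7.1.3, 7.3).**

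| Group | Items of 7.1.2.1 | Count |
|---|---|---|
| Match Week 72 | ECG; weight and oxygen saturation; physical examination and vital signs; pregnancy test; safety labs; AE/SAE; concomitant medications; seizure diary; hospital log; CarerQoL-7D; PedsQL; dosing at the visit (item 8, matched to the in-office dosing row that Table 2 marks at Week 72) | 12 |
| Baseline only | Screening review; randomization; dispensing | 3 |
| Differs | PK: five timepoints against one | 1 |

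12 + 3 + 1 = 16. The match for item 8 is a judgement, because its wording concerns the first dose. The PK conflict does not depend on it.

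Three Week 72 items are not in 7.1.2.1: EEG, dosing-diary review and bottle reconciliation.

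**3. Extra blood under the literal reading.** Inputs from Protocol 7.4.2: safety labs about 8 mL per visit; PK visit about 18 mL at 10 kg or more and about 12 mL under 10 kg. The assumption is that the PK-visit figures include the 8 mL of safety labs.

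- Volume per PK sample, 10 kg or more: (18 − 8) / 5 = 2 mL.
- Volume per PK sample, under 10 kg with two timepoints: (12 − 8) / 2 = 2 mL.
- Extra at 10 kg or more: (5 − 1) × 2 = 8 mL. The visit takes 18 mL instead of 8 + 2 = 10 mL.
- Extra under 10 kg: (2 − 1) × 2 = 2 mL. The visit takes 12 mL instead of 10 mL.

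Both stay within the stated maximum for a PK visit (18 and 12 mL).

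The equal 2 mL in both weight groups supports the assumption. If the PK figures excluded safety labs, a sample would be 18 / 5 = 3.6 mL in larger children and 12 / 2 = 6 mL in smaller ones, which is implausible. The extra would then be 4 × 3.6 = 14.4 mL and 1 × 6 = 6 mL.

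**4. Which list was intended for Week 72.** The stated maximum totals (about 100 and 88 mL) differ by 12 mL. Each serial PK visit contributes 18 − 12 = 6 mL to that gap. So 12 / 6 = 2 serial visits, which are Baseline and Week 24. A third at Week 72 would give 3 × 6 = 18 mL. The blood budget therefore agrees with footnote i, not with the reference to 7.1.2.1.

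**The case against.** The strongest reply is that a sensible site will find the right content. Section 7.1.11 begins by asking for the end-of-treatment assessments, and 7.1.10 places that visit at Week 72, so a site can turn to the Week 72 column of Table 2. Section 7.1.10 says that the visit includes the 7.1.2.1 assessments, not that it is limited to them. Some of the missing content is partly covered: 5.2.1 requires drug supplies to be returned or destroyed after accountability, 5.4 has compliance reviewed on an ongoing basis, and 6.2 asks for evaluation of subjects who do not complete. Table 2 has a single row for both diaries, marked at Baseline as well. Section 7.1.2.1 may name only the seizure diary because dosing entries start after the first dose.

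Much of this stands, and it limits the consequences. It does not make the reference correct. A non-exclusive list can be extended to hold an EEG, but it cannot reconcile five PK timepoints with a single 4-hour sample. The route to the Week 72 column also requires a site to set aside the section that both paragraphs name.

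Three stronger readings are tempting, and the documents do not support them:

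- A reader might infer that completers will have serial PK at Week 72. Table 2, footnote i, 7.1.3 and 7.3 set one sample there, and specific text should prevail.
- A reader might infer that departing subjects are to be randomized or supplied with drug. Sections 7.1.10 and 7.1.11 import assessments, whereas 7.1.2.1 introduces its list as assessments and procedures. No site would read it that way in practice.
- A reader might blame the reference for the lack of guidance on dose-timed ECG and PK in a subject already off drug. The Week 72 list is equally silent, so that is a separate question.

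**Conclusion.** Wrong as written, minor. The cross-reference in 7.1.10 and 7.1.11 names the wrong list. At Week 72 other text largely settles the matter. At early termination nothing else sets the content, so the wrong list is the operative one.

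The size, per early terminator, is four extra PK samples at 10 kg or more, or one extra under 10 kg on the reduced schedule. The volumes rest on the assumption that the PK-visit figures include safety labs. The number of early terminators is not given, so no trial-level total can be stated.

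The three omitted items have limited analytic weight. SAP 6.5 only lists EEG by subject, and SAP 4.6 computes drug compliance from diary entries, not from returned bottles. The primary endpoint comes from daily seizure-diary counts, and 7.1.2.1 does include the seizure-diary review. The primary analysis, type I error and power are therefore unaffected.

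**What to change.** In 7.1.10 and 7.1.11, change the cross-reference from 7.1.2.1 to the Week 72 items of 7.1.3 and Table 2. Add an early-termination column to Table 2 that marks EEG, review of both diaries and bottle reconciliation, and leaves out serial PK, randomization and dispensing.

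The cost is two corrected references and one table column in the next amendment. Sample size and analysis do not change.

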7.2. Efficacy Assessments

Efficacy assessments will include numbers of motor and non-motor seizures, which should be recorded at least daily in the electronic diary.

The number of emergency room visits, use of rescue seizure medications, and health-related quality of life as measured by the CarerQoL-7D and PedsQL questionnaires, will also be captured in the electronic diary or recorded on the appropriate page of the eCRF.

7.3. PK and/or Other Assessments

Blood samples for PK assessments will be drawn predose and 1, 3, 4, and 8 hours postdose (prior to the next dose of study drug) at Baseline and Week 24, and 4 hours postdose at Week 48 and Week 72. For subjects weighing less than 10 kg, PK blood draw can be reduced to 2 timepoints per visit at the Baseline and Week 24 visits. Recommended timepoints are 0 (predose) hour and 4 hours postdose. The collection of these drug concentration values will serve 2 purposes: (1) to assess the consistency of systemic drug concentrations at specific timepoints around the time to maximum plasma concentration to confirm the durability of drug exposure and (2) be potentially incorporated in a structural model (from prior PK profiles) that can help to quantitate selected pharmacodynamic relationships such as safety and disease improving effects.

7.4. Safety Evaluations

Safety will be evaluated by physical examinations, vital signs assessments, 12-lead ECGs, EEGs, routine clinical laboratory tests (including blood chemistry, hematology, coagulation, and urinalysis as described below), and AE assessments from baseline through study completion. Serious adverse events will be collected from the time of obtaining informed consent through the end of the follow-up phase.

If at any time during the treatment phase of the study, in the opinion of the investigator, a finding of an AE precludes continuation of treatment with study drug at the dose level at which the AE was observed, the dose and/or dose regimen for the study drug may be reduced or terminated altogether at the discretion of the investigator. The investigator will inform the sponsor of any discontinuations of treatment with vatiquinone and the DSMB will be notified of all AEs and SAEs. The investigator may solicit advice of the sponsor at any time to ensure the safety and well-being of participating subjects.

7.4.1. Physical Examination, Height, Weight, and Vital Signs

Complete physical exams will be conducted (excluding genital/rectal exam) at protocol specified study visits. The physical examination will consist of an examination of the following: general appearance, skin, head, eyes, ears, nose, throat, neck (including thyroid), lymph nodes, chest, heart, abdomen, and extremities.

Medical history and demographics including age, gender, and race, will be collected at the Screening Visit. Weight (lb or kg) will be measured in ordinary indoor clothing (ie, street clothes, scrubs, etc) with shoes off. Height will be recorded in centimeters or inches.

If clinically significant findings, as determined by the investigator, are recorded for a particular symptom, sign, or abnormal measurement, that measurement will be repeated at medically appropriate intervals until the value returns to an acceptable range, a specific diagnosis is established, or the condition is otherwise explained.

Vital sign measurements (pulse rate, blood pressure, and respiration rate) will be obtained in the sitting position (after the subject has been sitting for 5 minutes, if the subject is capable of sitting for 5 minutes).

7.4.2. Laboratory Evaluations

The maximum total quantity of blood that will be collected during a subject's participation in the MIT-E study will be approximately 100 mL for subjects weighing 10 kg or more and approximately 88 mL for subjects weighing less than 10 kg. The maximum volume that will be collected per visit will be approximately 8 mL for safety laboratory assessments and 18 mL during PK visits for subjects weighing 10 kg and over.

The maximum volume that will be collected per visit will be approximately 8 mL for safety laboratory assessments and approximately 12 mL during PK visit for subjects weighing less than 10 kg.

The maximum total volume (if a subject is rescreened) that could be withdrawn is approximately 107 mL in the case of a subject weighing 10 kg or more and approximately 95 mL in the case of a subject weighing less than 10 kg.

Refer to Section 7.1 (Table 2), Section 7.1.2.1, Section 7.1.2.8, and Section 7.3 for modified PK collection for subjects weighing less than 10 kg. Urine will also be collected at specified timepoints for analysis.

The following variables will be collected at various times to assess safety.

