7.1.2.8. Week 24 Clinic Visit (Days 168 ± 1 week)

The following assessments and procedures will be performed at Week 24 (±1 week):

1. 12-lead ECG at 4 hours postdose time-matched to PK blood collection; ECG should be performed approximately within 10 minutes preceding the 4-hour PK blood collection
2. Weight and oxygen saturation
3. Physical Examination including vital signs
4. Urine pregnancy test: WOCBP must have a negative urine pregnancy test (see Section 7.4.3). If a subject cannot perform a urine pregnancy test, a serum pregnancy test should be performed.
5. Laboratory assessments for hematology, coagulation, serum chemistry, and urinalysis (See Section 7.4.2)
6. Blood samples drawn for PK analysis predose and 1, 3, 4, and 8 hours postdose (prior to the next dose of vatiquinone). For subjects weighing less than 10 kg, PK blood draw can be reduced to 2 timepoints per visit. Recommended timepoints are 0 (predose) hour and 4 hours

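### The blood-volume maxima in Protocol 7.4.2 for subjects under 10 kg fit only a two-timepoint PK draw, which every PK passage leaves optional

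*Protocol*

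**What the plan says.** Protocol Section 7.4.2 sets maxima by weight class.

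- Per visit, 10 kg and over: "approximately 8 mL for safety laboratory assessments and 18 mL during PK visits for subjects weighing 10 kg and over".
- Per visit, under 10 kg: about 8 mL for safety laboratories and "approximately 12 mL during PK visit for subjects weighing less than 10 kg".
- Whole study: "approximately 100 mL for subjects weighing 10 kg or more and approximately 88 mL for subjects weighing less than 10 kg".
- Whole study with rescreening: "approximately 107 mL in the case of a subject weighing 10 kg or more and approximately 95 mL in the case of a subject" under 10 kg.

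For the modified PK collection under 10 kg, the section refers the reader to Table 2 and Sections 7.1.2.1, 7.1.2.8 and 7.3. It adds no sampling rule of its own.

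The general PK schedule at Baseline and Week 24 has five samples. Table 2 footnote i reads: "Blood will be drawn for PK assessment predose and 1, 3, 4, and 8 hours postdose". For the lighter subjects, Section 7.1.2.8 (Week 24) says: "For subjects weighing less than 10 kg, PK blood draw can be reduced to 2 timepoints per visit". Section 7.3 says that the "PK blood draw can be reduced to 2 timepoints per visit at the Baseline and Week 24 visits". Section 7.1.2.1 (Baseline), Table 2 footnote i and SAP Appendix 1 footnote i use the same permissive verb. At Weeks 48 and 72 one sample is taken at every weight.

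**The concern.** Section 7.4.2 gives a lower maximum under 10 kg, and the only thing in the documents that could lower the volume is the reduced PK sampling. If that reduction is optional, the stated maximum is not one that the schedule guarantees. A site can keep all five timepoints in a very small child, find nothing in the PK passages against it, and still exceed the volume that Section 7.4.2 says will not be passed.

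The group is foreseen by the plan. There is no lower age limit, inclusion criterion 6 makes specific provision for subjects under 2 years, and the dosing table (Protocol Table 1) starts at 4 kg. Section 9.1.9 lists failure to adhere to PK blood draw requirements among its examples of deviations, so sites and monitors need to know which requirement applies. This is a safety and consistency matter. It does not touch the primary endpoint, the error rate or the power.

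**Working it through.** **Inputs (Protocol 7.4.2 unless noted)**

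- Safety laboratories: about 8 mL per visit, both weight classes.
- PK visit: 18 mL (10 kg and over), about 12 mL (under 10 kg).
- Totals: about 100 and 88 mL; with rescreening about 107 and 95 mL.
- PK samples at Baseline and Week 24: 5 on the full schedule, 2 on the reduced one (Table 2 footnote i).
- PK samples at Weeks 48 and 72: 1 each.
- Full safety draws: 9 (Baseline and Weeks 4, 8, 12, 24, 36, 48, 60, 72, from Table 2).

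No passage states the volume of a PK sample, so it has to be inferred.

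**Step 1. Reproduce the per-visit figures.** Let *s* be the safety volume and *p* the volume per PK sample.

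- 18 = *s* + 5*p* and 12 = *s* + 2*p*
- Subtracting: 6 = 3*p*, so *p* = 2 mL and *s* = 8 mL.

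The solved *s* equals the stated 8 mL, so both maxima are reproduced exactly: 8 + 5×2 = 18 and 8 + 2×2 = 12.

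**Step 2. Check against the gap between totals.**

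- Stated gaps: 100 − 88 = 12 mL and 107 − 95 = 12 mL.
- Expected from the reduction: 2 visits × 3 omitted samples × 2 mL = 12 mL.

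The match is exact. The totals under 10 kg therefore assume the reduction at both Baseline and Week 24.

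**Step 3. Rebuild the totals.** The screening draw implied by rescreening is 107 − 100 = 95 − 88 = 7 mL. With *k* timepoints at Baseline and Week 24,

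total = 7 + 9*s* + 2×(2*k* + 2).

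| Safety draw *s* | *k* = 5 | *k* = 2 | *k* = 5, rescreened | *k* = 2, rescreened |
|---|---|---|---|---|
| 8 mL | 103 | 91 | 110 | 98 |
| 7.67 mL (assumed; rounds to 8) | 100 | 88 | 107 | 95 |
| Stated | 100 | 88 | 107 | 95 |

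At exactly 8 mL the rebuilt totals are 3 mL high. A safety draw of 7.67 mL removes that difference. The 12 mL gap is the same in either case.

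**Step 4. Test the other reading.** Suppose that 18 and 12 mL come on top of the 8 mL.

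- Volume per sample: 18/5 = 3.6 mL in one class and 12/2 = 6.0 mL in the other.
- Totals: 7 + 72 + 2×18 + 2×3.6 = 122.2 mL and 7 + 72 + 2×12 + 2×6 = 115 mL.

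These do not fit the stated 100 and 88 mL, so this reading fails.

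**Step 5. Volumes if a subject under 10 kg is not reduced to two timepoints.**

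| Timepoints | Volume at Baseline or Week 24 | Against 12 mL |
|---|---|---|
| 2 | 8 + 4 = 12 mL | 0 |
| 3 | 8 + 6 = 14 mL | +17% |
| 4 | 8 + 8 = 16 mL | +33% |
| 5 | 8 + 10 = 18 mL | +50% |

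- With *s* = 7.67 mL the five-sample excess is 17.67/11.67 − 1 = 51%.
- Whole study, five samples at both visits: 88 + 12 = 100 mL (100/88 − 1 = +13.6%).
- With rescreening: 95 + 12 = 107 mL (107/95 − 1 = +12.6%).
- Weeks 48 and 72: 8 + 2 = 10 mL, within the 12 mL.

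**The case against.** The best defence is that the passages can be read together. Section 7.4.2 is protocol text of equal standing and states a maximum. The PK passages allow departure from five samples, Section 7.4.2 caps the volume, and a site that takes two samples satisfies both. The stated figures are also sound for the two-sample scheme, so nothing is miscalculated.

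Much of this stands. It corrects a stronger reading that a reader might infer: that the protocol authorises a draw 50% over its own limit. It does not, because a five-sample draw would exceed Section 7.4.2. But reading 7.4.2 as a cap does not remove the problem. The PK passages then permit what the cap forbids, and the cross-reference from 7.4.2 leads only to passages that make the reduction optional.

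A second defence is that every figure under 10 kg is approximate, that the 2 mL is inferred, and that Section 7.1.6 sends collection to a laboratory manual not available here, which may set sample volumes. The inference should be labelled as such. Approximation can cover the 3 mL in the rebuilt totals; it cannot absorb about 50% at a visit.

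Third, the PK passages call predose and 4 hours recommended timepoints, and a reader might take this as further evidence that the number of samples is optional. It is not: the phrase says which two timepoints to use. Only the permissive verb supports the point.

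Finally, a reader might infer that leaving the choice open harms the PK analysis by mixing five-point and two-point profiles. The documents do not show this. SAP Section 6.7.1 summarises concentrations by visit and timepoint and leaves the PK analysis to a separate document. Nor do the documents give a limit in mL/kg against which a per-kilogram volume could be judged.

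**Conclusion.** Wrong as written, as an internal inconsistency. The maxima for subjects under 10 kg hold only if PK sampling is cut to two timepoints at both Baseline and Week 24, and no passage requires that cut. A five-sample draw complies with the PK passages and gives about 18 mL against about 12 mL, roughly 50% over, at those two visits. Over the study it gives about 100 mL against 88 mL, or 107 against 95 mL with rescreening.

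The size rests on an inferred PK sample volume of about 2 mL that is the same in both weight classes. Both per-visit maxima, with the stated 8 mL, and the 12 mL gap between the totals agree with that value. The excess is possible, not certain: it arises only if a site does not use the offered reduction. The documents do not say how many subjects under 10 kg are expected.

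**What to change.** Reconcile Protocol Section 7.4.2 with Table 2 footnote i, Sections 7.1.2.1, 7.1.2.8 and 7.3, and SAP Appendix 1 footnote i, so that the sampling permitted for subjects under 10 kg cannot exceed the maximum volumes stated for them. Which passage governs is a clinical decision for the sponsor, and this review proposes neither a sampling rule nor a volume. Stating the volume per PK sample in Section 7.4.2 would let a reader check the maxima directly.

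The cost is a few words in a protocol amendment, the matching SAP footnote and, if it repeats the rule, the laboratory manual. No efficacy analysis changes.
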